5.3. Change from Baseline Definitions

Definition	Reporting Details
Change from Baseline	=Post-Biopsy Value – Baseline
% Change from Baseline	= $100 \times [(Post\text{-}Biopsy Value - Baseline) / Baseline]$

5.4. Examination of Covariates, Other Strata and Subgroups

5.4.1. Covariates and Other Strata

The list of covariates may be used in descriptive summaries and statistical analyses. Additional covariates and other strata of clinical interest may also be considered.

Category	Details
Covariates	Age, Gender, Site

NOTES:

- The effect of Age/Gender will be explored if it was not possible to match all subjects by age and gender.
- The effect of site will be explored

5.4.2. Examination of Subgroups

No planned subgroups will be examined.

5.5. Multicentre Studies

There are no planned adjustments made for multiple centres in this study.

5.6. Multiple Comparisons and Multiplicity

There are no planned adjustments for multiple comparisons or multiplicity.

5.7. Other Considerations for Data Analyses and Data Handling Conventions

Other considerations for data analyses and data handling conventions are outlined in the appendices:

Table 1 Overview of Appendices

Section	Component
10.3	Appendix 3 : Data Display Standards & Handling Conventions
10.4	Appendix 4 : Derived and Transformed Data
10.5	Appendix 5 : Premature Withdrawals & Handling of Missing Data
10.6	Appendix 6 : Values of Potential Clinical Importance
10.7	Appendix 7 : Model Checking and Diagnostics for Statistical Analyses
10.8	Appendix 8 : Biomarker Analyses

6. STUDY POPULATION ANALYSES

6.1. Overview of Planned Analyses

The study population analyses will be based on the enrolled population, unless otherwise specified.

Study population analyses including analyses of subject's disposition, protocol deviations, demographic and baseline characteristics, prior and concomitant medications, will be based on GSK Core Data Standards.

The number and percent of subjects will be reported for the responses for the categorical Pre-Biopsy and Post-Biopsy lymph node questionnaire data. All questions will be listed.

Details of the planned displays are presented in [Appendix 10: List of Data Displays](#)

6.1.1. Interim Analysis 1

No study population analyses will be produced for the first interim analysis.

6.1.2. Interim Analysis 2

No study population analyses will be produced for the first interim analysis.

7. PRIMARY STATISTICAL ANALYSES

7.1. Biomarker Analyses

7.1.1. Overview of Planned Biomarker Analyses

The primary biomarker analyses will be based on the ‘Safety’ population, unless otherwise specified.

Between group (HV vs NOT1D) comparisons will use data from all subjects who have at least one evaluable sample from either method. Between method comparisons and analyses will only be performed in subjects who provide sufficient cells from both methods in each pairwise comparison (as shown in [Figure 1](#)).

If sufficient numbers of cells to meet the cell number requirements of the primary endpoint are obtained by both biopsy methods, the primary endpoint analysis will be carried out independently for each biopsy method, otherwise only the biopsy method for which sufficient numbers of cells were obtained will be used for primary analysis.

Details of the planned displays are presented in [Appendix 10: List of Data Displays](#)

For biomarkers that indicate a difference between methods or groups, further explanatory analyses may be carried out to explore correlations between biomarkers or the impact of covariates.

7.1.1.1. Interim Analyses 1

Summary statistics and a listing for the overall cell counts will be presented.

7.1.1.2. Interim Analyses 2

All primary and secondary comparisons will be presented, as detailed in [Appendix 10: List of Data Displays](#)

7.1.2. Planned Biomarker Statistical Analyses

Primary Statistical Analyses
Endpoint(s)

 • Proportion of flow cytometry cell counts
Model Specification

 • Endpoints analyzed for each flow cytometry cell type using generalized linear mixed models (GLMM). 
The analysis will be performed on the parameters listed in
 
 • Appendix 8: Biomarker Analyses • Terms in GLMM model will include: 
 Fixed categorical: group, sample type, and the interaction of group with sample type Random effect: subject Where group is either HV or NOT1D, and sample type is peripheral blood, core biopsy or fine needle aspirate.
Model Checking & Diagnostics

Refer to
 
 • Appendix 7: Model Checking and Diagnostics for Statistical Analyses
Model Results Presentation

 • For proportional cell counts, these models will estimate the mean (or geometric mean) proportion for each sample type in each group, comparing means using differences or ratios as outlined in the primary hypothesis section.

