8.2.2. Sample Size Sensitivity

No formal sample size sensitivity analysis has been performed.

The precision for iLN estimates is expected to be lower than the precision for PBMC estimates, since it is anticipated that fewer cells will be available from iLN biopsies for flow cytometry analysis. No published data was found for the phenotypes of interest in iLN biopsies.

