8.4. Key Elements of Analysis Plan

8.4.1. Primary Analyses

Descriptive statistics will be calculated for each of the primary flow cytometry cell types by group and sample type (blood / core biopsy / fine needle aspirate biopsy). The flow cytometry data for each cell type will be displayed graphically using scatter plots of cell count and % cell count versus group and/or sample type.

Generalized linear models with appropriate link functions will be used to analyze data separately for each flow cytometry cell type. Models will include terms for group, sample type, and the interaction of group with sample type. Subject will be included as a random effect term.

- For absolute cell counts, these models will estimate the mean cell count for each sample type in each group, comparing means as outlined in the primary hypothesis section.
- For proportional cell counts, these models will estimate the average odds (or relative risk) of having a particular cell type for each sample type in each group, comparing these odds (or relative risks) by estimating the ratios for the primary comparisons of interest.

All estimates will be presented with 95% confidence intervals.

Model assumptions will be checked, and modifications to the model or alternative approaches may be considered in the event of significant deviations from model assumptions.

Further details will be provided in the Reporting and Analysis Plan (RAP).

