10.5.2.3. Handling of Missing Data for Statistical Analysis

Missing data will remain missing with no imputation applied for the purposes of statistical analysis.

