10.7. Appendix 7: Model Checking and Diagnostics for Statistical Analyses

10.7.1. Statistical Analysis Assumptions

Endpoint(s)	
• Proportion of flow cytometry cell counts
Analysis	
• GLMM

• Model assumptions will be applied, but appropriate adjustments maybe applied based on the data.• The Kenward and Roger method for approximating the denominator degrees of freedom and correcting for bias in the estimated variance-covariance of the fixed effects will be used.• An unstructured covariance structure for the R matrix will be used by specifying 'type=UN' on the RANDOM line.
○ In the event that this model fails to converge, alternative correlation structures may be considered such as CSH or CS.○ Akaike's Information Criteria (AIC) will be used to assist with the selection of covariance structure.• Distributional assumptions underlying the model used for analysis will be examined by obtaining a normal probability plot of the residuals and a plot of the residuals versus the fitted values (i.e. checking the normality assumption and constant variance assumption of the model respectively) to gain confidence that the model assumptions are reasonable.• If there are any departures from the distributional assumptions, alternative models will be explored using appropriate transformed data.	

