10.8.2.6. General Derivations

For the parameters in Section 10.8.2.1, Section 10.8.2.2 and Section 10.8.2.3, the percentages will be transformed into counts by multiplying by the denominator counts / 100. The denominator counts are given in brackets in the test analyte column.

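### The final RAP allows geometric means, ratios and transformed data for the primary percentages but has no rule for a sample with zero events; if such samples fall out, rare-subset estimates are biased, and a model on the counts already derived avoids this.

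*SAP*

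**What the plan says.** The SAP file holds an interim RAP followed by the final RAP. This point concerns the final one.

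- **Planned estimand.** In protocol 8.4.1, for proportions, "these models will estimate the average odds (or relative risk) of having a particular cell type for each sample type in each group". Odds and relative risks estimated from counts accept a count of zero.
- **Final RAP 7.1.2.** The model is a generalized linear mixed model (GLMM) per cell type with no named distribution or link. For proportional counts, "these models will estimate the mean (or geometric mean) proportion for each sample type in each group, comparing means using differences or ratios". Section 2.1 does not list this as a change from the protocol.
- **Final RAP 10.7.1.** The checks are a normal probability plot and a constant-variance plot of residuals, with Kenward-Roger degrees of freedom and an unstructured R matrix. Then: "If there are any departures from the distributional assumptions, alternative models will be explored using appropriate transformed data".
- **Final RAP 10.8.2.6.** For the three flow panels, "the percentages will be transformed into counts by multiplying by the denominator counts / 100". No text makes these counts the model response.
- **Final RAP 10.5.2.3.** "Missing data will remain missing with no imputation applied for the purposes of statistical analysis". The only below-limit rule, in 10.4.3, is for safety laboratory values.
- **Protocol 8.2.2.** Compared with blood, "it is anticipated that fewer cells will be available from iLN biopsies for flow cytometry analysis".

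**The concern.** Section 10.7.1 reads like a normal-theory mixed model on the percentage itself. Rare percentages with many zeros are likely to fail its checks, and the usual next step for a geometric mean or a ratio is to log the response. The interim shell PD_T2 (page 2) already shows an LS mean ratio for the node, FNA and core comparisons with blood, and for FNA versus core. A sample with 0 events has no log. Unless someone decides otherwise, the software drops it.

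Sparse samples are credible. Section 10.8.2.2 lists deeply nested subsets, such as PD-1+ ICOS+ cells among Treg Tfh. Section 2.1 reports that exploratory objectives 2 to 5 were abandoned for lack of cells. The threshold of 1×10^6 cells in 3.1.1 is a total yield for continuing the study, not a minimum parent count per subset.

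At stake are the primary estimates and their 95% intervals. There is no multiplicity adjustment, and section 7.1.1 lets apparent differences lead to further analyses.

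**Working it through.** The plan gives no figure for this point. Its one precision figure (protocol 8.2.1, blood regulatory T cells) cannot be rebuilt because its inputs are not given, and it is not used here.

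**Small example.** Three samples have 3, 1 and 0 events out of 100. The arithmetic mean is (3+1+0)/3 = 1.33%. The geometric mean is 0 with the zero kept and √(3×1) = 1.73% with it dropped.

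**Inputs.** From the documents: up to 15 per group (protocol 8.2), 95% intervals (protocol 8.4.1), and fewer node cells than blood cells (protocol 8.2.2). Assumed: expected events per sample λ from 0.5 upwards; between-subject log SD 0.5, with 0.8 as a check; true HV versus NOT1D ratio 2; true method ratio 1 with a 10-fold denominator difference. Events are Poisson with mean λ·exp(u), u ~ N(0, SD²).

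**Step 1: one sample type, zeros dropped.** Let b(λ) be the geometric mean of the retained samples divided by the true one (log SD 0.5).

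| λ | zeros | b(λ) |
|---|---|---|
| 0.5 | 59% | 2.53 |
| 1 | 37% | 1.56 |
| 2 | 16% | 1.11 |
| 3 | 8% | 0.99 |
| 5 | 2% | 0.94 |
| 10 | 0.2% | 0.945 |

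**Step 2: group ratio.** Estimated ratio = 2 × b(λ in NOT1D) / b(λ in HV), with NOT1D taken as the higher group.

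- Equal denominators, λ = 0.5 in HV: 2 × 1.56/2.53 = 1.23.
- λ = 1: 2 × 1.11/1.56 = 1.42 (1.43 when simulated directly).
- Direct simulation gives 1.71 at λ = 2, 1.88 at 3 and 2.02 at 5.
- In a separate binomial simulation with 15 per group, 95% interval coverage was about 55%, 77% and 92% at λ = 0.5, 1 and 2.
- With log SD 0.8 the ratio is 1.27, 1.43, 1.64, 1.77, 1.91 and 2.01 at λ = 0.5, 1, 2, 3, 5 and 10, so the bias lasts until about 5 to 10 events.
- NOT1D denominators 5-fold smaller: 3.88 at λ = 1 and 3.23 at λ = 2. Five-fold larger: 1.21 and 1.75. The direction is not fixed.

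**Step 3: paired methods, true ratio 1.** Pairs with a zero are dropped, and the ratio is exp(mean of log y₁ − log(y₂/10)).

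| λ, sparse sample | ratio | 95% CI excludes 1 |
|---|---|---|
| 0.5 | 2.28 | 61% |
| 1 | 1.44 | 30% |
| 2 | 1.06 | 6% |
| 3 | 0.97 | 5% |
| 5 | 0.93 | 7% |

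A binomial version with within-subject log SD 0.2 gave 2.31, 1.47 and 1.08 at 0.5, 1 and 2. There, pooled events over pooled parent cells gave 1.00 to 1.03, so the false difference comes from the discarded zeros. With equal denominators and λ = 1 the ratio is 1.00.

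**Step 4: counts kept.** A log-link Poisson mixed model that retains zeros (15 per group, 500 runs) gave median ratios of 1.96, 1.98, 2.04, 2.02 and 1.97 for a true 2 at λ = 1, 2, 3, 5 and 20. Dropping zeros in the same runs gave 1.40, 1.71, 1.88, 2.03 and 2.03. Adding 0.5 to the events, in the binomial between-group simulation, gave only 1.46, 1.71 and 1.90 at λ = 0.5, 1 and 2.

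**Scale, on assumed fractions.** Suppose one third of the yield goes to the panel, 40% of that is CD4, 5% of those are Treg and half of those are memory. Then 10^6 cells give 10^6 × 1/3 × 0.4 × 0.05 × 0.5 = 3,333 memory Tregs. A subset at 1% has 33 expected events and one at 0.1% has 3.3. At 10^5 cells these become 3.3 and 0.33.

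**The case against.** The strongest reply is that nothing here is a stated plan. The geometric mean is one of two options. The HV versus NOT1D column of interim shell PD_T2 shows a difference, the final figure titles refer to LS mean differences, and the final shells are not in the document. Section 10.7.1 names no log, and a transform that cannot take the observed values is hardly an appropriate one. A GLMM for a proportion of cell counts, with counts derived in 10.8.2.6, is naturally read as events over denominator. All of this stands against saying that the RAP commits to geometric means. It does not close the gap, because no sentence selects the count model and the 10.7.1 checks describe a different one.

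A reader might also infer that 10.5.2.3 turns zeros into missing values. It does not: 10.5.2 defines missing data as requested data that were not supplied, and a recorded 0% was supplied. Dropping would be a by-product of taking logs, not a rule.

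Four further limits stand:

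- Shrinkage of the group ratio is not general; it needs similar denominators in both groups.
- A false FNA-versus-core difference needs unequal yields. Protocol 8.2.2 compares node with blood only.
- Pooling turns on meaningful differences, not on an interval excluding 1, and with objectives 2 to 5 not evaluated it bears at most on exploratory objective 1.
- Method comparisons are limited to subjects with sufficient cells. That may remove some sparse pairs, but sufficient is not quantified in 7.1.1.

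**Conclusion.** The concern holds conditionally. The final RAP leaves open a log-percentage analysis that cannot take an observed 0%, departs from the odds or relative risks of protocol 8.4.1, and does not use its own derived counts as the response. If logs are taken and zero-event samples fall out, bias is material below about 3 expected events per sample (about 5 to 10 with log SD 0.8). At 0.5 to 2 expected events, a true group ratio of 2 is estimated as about 1.2 to 1.7 with similar denominators, and in either direction with unequal ones. A false node-versus-blood ratio of about 2.3 or 1.45 (0.5 or 1 expected event) can come from yield alone under a 10-fold denominator difference.

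The spreads, event rates and denominator ratios are assumptions. The number of affected parameters among the 70 (22 + 30 + 18 in 10.8.2.1 to 10.8.2.3) is unknown and could be small. The documents do not support saying that zeros will be dropped, that group ratios always shrink, or that a false FNA-versus-core difference is to be expected.

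**What to change.** 1. In 7.1.2, analyse each percentage as events out of denominator, using the 10.8.2.6 counts, in a logit- or log-link GLMM with subject and sample-level overdispersion terms. Report odds ratios or relative risks as in protocol 8.4.1.
2. In 10.5.2.3, state that an observed 0% with a non-zero denominator is data and is retained.
3. In 10.7.1, limit any log-transformed fallback to parameters with no zero-event sample. Adding 0.5 to the events is not a sufficient substitute.
4. Report the number of zero-event samples by group and sample type for each parameter.

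Cost: the counts and denominators are already derived, so the programming change is modest. Intervals for the rarest subsets will be wider, and some models will need a simpler covariance structure to converge. The normal-residual, Kenward-Roger and covariance text in 10.7.1 must be adapted to a count model. The count model was checked here by maximum likelihood, for the group comparison only and from 1 expected event upwards, so its behaviour below that should be checked before it is relied on.

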8.2.1. Sample Size Assumptions

For PBMCs, literature data was available for lymphocytes CD4+, CD8+ and regulatory T-cells in HVs using a similar gating strategy to that planned here. Computer simulation were performed to assess the expected precision of estimation of odds ratios and relative risks for a cross sectional comparison of PBMC regulatory T-cells for a range of differences between NOT1D subjects and HVs. The average precision for both PBMC estimates is expected to be within 1% of the point estimate using n=15 per group

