7.1.2. Planned Biomarker Statistical Analyses

Primary Statistical Analyses
Endpoint(s)

• Proportion of flow cytometry cell counts
Model Specification

• Endpoints analyzed for each flow cytometry cell type using generalized linear mixed models (GLMM).• The analysis will be performed on the parameters listed in Appendix 8: Biomarker Analyses• Terms in GLMM model will include:
Fixed categorical: group, sample type, and the interaction of group with sample typeRandom effect: subjectWhere group is either HV or NOT1D, and sample type is peripheral blood, core biopsy or fine needle aspirate.
Model Checking & Diagnostics

• Refer to Appendix 7: Model Checking and Diagnostics for Statistical Analyses
Model Results Presentation

• For proportional cell counts, these models will estimate the mean (or geometric) cell count for each sample type in each group, comparing means using ratios as outlined in the primary hypothesis section.

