2. SUMMARY OF KEY PROTOCOL INFORMATION

2.1. Changes to the Protocol Defined Statistical Analysis Plan

Exploratory objectives 2-5 were not evaluated due to only a limited number of cells being available to analyze, as no data has been collected these have been removed from the RAP, except for Section 2 to maintain consistency with the protocol.

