2.4. Statistical Hypotheses

This study is designed to explore the phenotype of immune cells in the iLN and peripheral blood (such as, but not restricted to PBMCs) of NOT1D subjects compared to HVs.

There are no formal hypotheses being tested due to the exploratory nature of the study. Primary comparisons of NOT1D subjects to HVs will be made using an estimation approach, providing point estimates and confidence intervals.

Secondary comparisons of biopsy methods will be made within NOT1D subjects and HVs using an estimation approach:

[figure not shown]
- iLN biopsies will be carried out by two related methods, fine-needle aspirate (FNA) and core biopsy sampling:
- If sufficient numbers of cells to meet the cell number requirements of the primary endpoint are obtained by both biopsy methods, the primary endpoint analysis will be carried out independently for each biopsy method, otherwise only the biopsy

method for which sufficient numbers of cells were obtained will be used for primary analysis.

- If no meaningful differences between biopsy methods are observed, material from both biopsy methods may be pooled to meet exploratory objectives 1, 2, 3 and 4. Material from fine-needle aspirate and core biopsies will not be pooled unless supported by the comparison described above.
- If meaningful differences in the proportion of leukocyte subsets between cells derived from each biopsy method are observed, then:
 - If sufficient number of core biopsy derived cells are available, these will be analysed for exploratory objectives 1 and 2.
 - Fine needle aspirate derived cells will be used to meet exploratory objectives 3 and 4. If insufficient number of core biopsy derived cells are available to meet exploratory objectives 1 and 2, then fine needle aspirate derived cells may be used to meet either or both of those exploratory objectives.

A graphical representation of the comparisons are shown in [Figure 1](#).

Figure 1 - Graphical representation of comparisons

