10.10.7. Biomarker Figures

Biomarker: Figures					
No.	Population	IDSL / TST ID / Example Shell	Title	Programming Notes	Deliverable [Priority]
Frequency and phenotype of leukocyte subsets by flow cytometry					
2.01	Safety	PD_F1	Boxplots of B_DC_Monocyte Panel by Method and Patient Group	Parameters listed in Section 10.8.2.1	IA SAC, SAC
2.02	Safety	PD_F2	LS Mean Estimates and Differences with 95% CI of B_DC_Monocyte Panel	Parameters listed in Section 10.8.2.1	IA SAC, SAC
2.03	Safety	PD_F1	Boxplots of T Cell Panel by Method and Patient Group	Parameters listed in Section 10.8.2.2	IA SAC, SAC
2.04	Safety	PD_F2	LS Mean Estimates and Differences with 95% CI of T Cell Panel	Parameters listed in Section 10.8.2.2	IA SAC, SAC
2.05	Safety	PD_F1	Boxplots of Treg Panel by Method and Patient Group	Parameters listed in Section 10.8.2.3	IA SAC, SAC
2.06	Safety	PD_F2	LS Mean Estimates and Differences with 95% CI of Treg Panel	Parameters listed in Section 10.8.2.3	IA SAC, SAC
2.07	Safety	PD_F1	Boxplots of ratios of effector cells to regulatory cells by Method and Patient Group	Parameters listed in Section 10.8.2.4	IA SAC, SAC
2.08	Safety	PD_F2	LS Mean Estimates and Differences with 95% CI of ratios of effector cells to regulatory cells	Parameters listed in Section 10.8.2.4	IA SAC, SAC
Suppressive activity of regulatory cells					
2.09	Safety	PD_F1	Boxplots of Suppressive activity of regulatory cells by Method and Patient Group	Parameters listed in Section 10.8.2.5	IA SAC, SAC
2.10	Safety	PD_F2	LS Mean Estimates and Differences with 95% CI of Suppressive activity of regulatory cells	Parameters listed in Section 10.8.2.5	IA SAC, SAC

ICH : Listings					
No.	Population	IDSL / TST ID / Example Shell	Title	Programming Notes	Deliverable [Priority]
Subject Disposition					
1.	Screened	ES7	Listing of Reasons for Screening Failure		SAC
2.	Enrolled	ES2	Listing of Reasons for Subject Withdrawal		SAC
3.	Screened	ES9	Listing of Subjects who were rescreened		SAC
Inclusion / Exclusion Criteria					
4.	Enrolled	IE3	Listing of Eligibility Criteria Not Met		SAC
Protocol Deviations					
5.	Enrolled	DV2	Listing of Important Protocol Deviations		SAC
Populations Analysed					
6.	Screened	SP3	Listing of Subjects excluded from any population		SAC
Demographic Characteristics					
7.	Enrolled	DM2	Listing of Demographic Characteristics		SAC
8.	Enrolled	DM9	Listing of Race and Racial Combinations		SAC
Current and Past Medical Conditions					

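### Does leaving the primary comparison of cell proportions open to differences or ratios, without declaring a move away from odds ratios, call for a change to the final RAP?

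*SAP*

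**What the plan says.** Protocol 8.4.1 estimates, for proportions, the average odds or relative risk in each group and sample type, "comparing these odds (or relative risks) by estimating the ratios for the primary comparisons of interest". The simulation behind Protocol 8.2.1 was run "to assess the expected precision of estimation of odds ratios and relative risks". Section 8.4.1 also allows the model to be modified, or another approach used, if its assumptions clearly fail.

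The SAP document holds two plans. The interim RAP, section 7.1.2, speaks of "comparing means using ratios as outlined in the primary hypothesis section", while its mock table PD_T2 shows a difference between groups and a ratio between sampling methods. The final RAP, section 7.1.2, estimates a mean or geometric mean proportion, "comparing means using differences or ratios as outlined in the primary hypothesis section". Its section 2.4 says only "Primary comparisons of NOT1D subjects to HVs will be made using an estimation approach, providing point estimates and confidence intervals" and names no scale in the text; Figure 1 is not reproduced in the copy reviewed.

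The final RAP's figure list (10.10.7) uses titles such as "LS Mean Estimates and Differences with 95% CI of B_DC_Monocyte Panel" for every panel. Its section 10.7.1 says "If there are any departures from the distributional assumptions, alternative models will be explored using appropriate transformed data". Section 2.1, on changes from the protocol, reports only that "Exploratory objectives 2-5 were not evaluated due to only a limited number of cells being available to analyze". Mock shells for the final analysis are available on request (10.11).

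**The concern.** Read side by side, the two documents appear to have swapped the primary effect measure without saying so. Odds do not reappear in the final RAP, and differences and geometric-mean ratios are new. One model is fitted per cell type, and 10.7.1 lets the transformation follow residual plots. The scale could therefore differ between the 70 panel parameters (22 + 30 + 18 in 10.8.2.1 to 10.8.2.3), and there is no multiplicity adjustment (5.6).

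The stake would be the study's rationale in Protocol 2.1: that changes in the lymph node (iLN) are distinct from those in blood. Whether two changes differ depends on how change is measured. If both tissues change and start from different levels, the group-by-sample-type term can vanish on one scale and not on another. A scale picked after seeing the data could then settle the answer.

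**Working it through.** **The plan's own figure.** The only design number tied to odds ratios and relative risks is in Protocol 8.2.1: precision within 1% of the estimate for blood regulatory T cells at 15 per group. No frequency, SD or cell count is given, so it cannot be reproduced. Read as a 95% half-width on the log scale, 1.96 × SD × √(2/15) = ln(1.01), it would need a between-subject log-SD of 0.00995 / (1.96 × 0.365) = 0.014. It does not help to choose a scale.

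**What changed in the text.**

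| | Protocol 8.4.1 | Final RAP 7.1.2 |
|---|---|---|
| Odds ratio | allowed | not named |
| Relative risk | allowed | kept, as a ratio of means |
| Geometric-mean ratio | not named | added |
| Difference | not named for proportions | added |

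The protocol did not fix one measure either.

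**Why scale can matter.** RR = p1/p0 and OR = [p1/(1−p1)] / [p0/(1−p0)]. Frequencies are assumed, because the documents give none.

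- Blood 40% to 50%, iLN 70% to 80%. Differences: +10 and +10 points. RR: 0.50/0.40 = 1.25 and 0.80/0.70 = 1.14. OR: 1.00/0.667 = 1.50 and 4.00/2.333 = 1.71. The change is equal, larger in blood, or larger in iLN.
- Blood 5% to 7.5%, iLN 20% to 30%. Differences: +2.5 and +10 points. RR: 1.50 and 1.50. OR: 1.54 and 1.71.
- Blood 5% in both groups, iLN 20% to 30%. Differences: 0 and +10 points. RR: 1.00 and 1.50. OR: 1.00 and 1.71. All three measures agree.

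**How often it would show.** Simulation with 15 per group, logit-normal proportions, blood-iLN correlation 0.5 and 20,000 replicates. The interaction is a two-sample t test on each subject's iLN-minus-blood value. Entries are the share of 95% intervals that exclude no interaction, at logit SD 0.3:

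| Blood; iLN | Difference | Log ratio | Logit |
|---|---|---|---|
| 40-50%; 70-80% | 5% | 36% | 22% |
| 5-7.5%; 20-30% | 98% | 5% | 15% |
| 5-7.5%; 15-17.5% | 5% | 71% | 59% |
| 5-5%; 20-30% | 99.9% | 98.5% | 99.7% |

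In each of the first three rows the frequencies make the interaction exactly zero on one scale. The fourth row is the pattern that Protocol 2.2.2 cites as precedent: a lymph-node change not detected in blood cells. At SD 0.5 that row gives 88%, 69% and 81%, in the same direction throughout.

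In the first row, log and logit intervals exclude zero in opposite directions within the same data set 0.6% of the time at SD 0.3, 18% at SD 0.2 and 0% at SD 0.5. This is a conflict between relative risk and odds ratio, which the protocol's own wording already permits.

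**The stated primary comparison.** For NOT1D against healthy volunteers within one sample type, the three scales disagree on whether the interval excludes no effect in 0-9% of data sets. With no group effect, each scale excludes no interaction about 5% of the time, and taking any of the three gives 7.5-9%.

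**The case for a change.** The best argument for acting is that, in an estimation study, the effect measure is the result. Protocol 8.4.1 allows a change of model after assumptions fail, whereas the final RAP leaves the scale open before any check. The second interim analysis was meant partly to inform the final RAP, so the wording was settled when some data could have been seen. A sentence in 7.1.2 and a line in 2.1 would remove the doubt cheaply.

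The textual part of this stands: the wording differs, 2.1 is silent, and the cross-reference supplies no scale in its text. The consequence is weaker.

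- The listed tables and figures (10.10.5, 10.10.7) name no group-by-sample-type contrast. A reader would only compare tissues informally.
- Choosing the scale subset by subset is something the text permits, not something it plans.
- There is an ordinary reading. The interim table used differences between groups and ratios between methods, and the final wording may simply bring the text into line with that. The final shells, which could confirm it, are not in the documents.
- Summaries, boxplots and listings are planned for every parameter, so readers can see both tissues on the raw scale.

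**Conclusion.** The departure in wording is real and small. One protocol option (relative risk) survives, the protocol left the choice between odds ratio and relative risk open, and the stated group comparisons hardly depend on scale (0-9% disagreement). The study tests no formal hypothesis and attaches no decision rule to these estimates, so no error rate is at risk; the exposure is to interpretation when iLN and blood changes are compared informally.

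Listing the wording in 2.1 would alter no result. Saying which comparison uses which scale is detail that analysts would ordinarily settle in the table shells. Forcing one scale, such as the logit, on all 70 parameters would cost fit for rare subsets and ease of reading, and statisticians could reasonably differ on it. No change to the plan follows.

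This rests on assumed frequencies, SDs of 0.2 to 0.5 and a simplified complete-data analysis in place of the mixed model. It would be less secure if the final report rested its main claim on a formal contrast of iLN change with blood change while both tissues changed from different starting levels.
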